1. INTRODUCTION

This Statistical Analysis Plan (SAP) Amendment 1 specifies definitions of analysis sets, key derived variables, and statistical methods for analysis of efficacy and safety for the Phase 3 study RIVAROXDVT3002 (also known as MARINER). This SAP Amendment 1 is based on the Protocol RIVAROXDVT3002 Amendment INT-3, INT-4, INT-5, INT-6 and the Protocol RIVAROXDVT3002 Amendment INT-7, finalized on March 31th, 2017. Unless the key analysis method for efficacy and/or safety needs to be updated, a SAP amendment will not take place, regardless of a protocol amendment. Titles, mock-ups and programming instructions for all statistical outputs (tables, figures, and listings) are provided in a separate document entitled Data Presentation Specifications (DPS).

An Independent Data Monitoring Committee (IDMC) will monitor safety during this study, review interim safety/efficacy results, and make a recommendation whether the study should be continued as planned, modified or terminated early for futility or safety. There is no plan to stop the study for the superiority of the primary efficacy outcome. Safety data to be reviewed by the IDMC periodically and additional details for the planned interim analysis are specified in the IDMC SAP, which is specifically prepared for IDMC reviews.

1.1. Trial Objectives

The primary objective is to assess the efficacy and safety of rivaroxaban, compared with placebo in the prevention of symptomatic venous thromboembolism [VTE] (lower extremity deep vein thrombosis [DVT] and non-fatal pulmonary embolism [PE]) and VTE-related death (death due to PE or death in which PE cannot be ruled out as the cause) post-hospital discharge in high-risk, medically ill patients.

The secondary objectives are to compare rivaroxaban with placebo in the following post-hospital discharge outcomes in high-risk, medically ill patients:

- VTE-related death (death due to PE or death in which PE cannot be ruled out as the cause)
- Symptomatic VTE (lower extremity DVT and non-fatal PE)
- The composite of symptomatic VTE (lower extremity DVT and non-fatal PE) and all-cause mortality (ACM)

- The composite of symptomatic VTE (lower extremity DVT and non-fatal PE), myocardial infarction (MI), non-hemorrhagic stroke and cardiovascular (CV) death (death due to a known CV cause and death in which a CV cause cannot be ruled out; by this definition, a VTE-related death is considered a CV death)
- All-cause mortality (ACM)

The exploratory objectives are to compare rivaroxaban with placebo, in the following post-hospital discharge outcomes in high-risk, medically ill patients:

- Symptomatic lower extremity DVT
- Symptomatic non-fatal PE
- Symptomatic upper extremity DVT
- MI
- Non-hemorrhagic stroke
- Re-hospitalization for symptomatic VTE (lower extremity DVT and non-fatal PE) within 30 days after randomization

The pharmacokinetic (PK) objective is to assess the kinetics of rivaroxaban in high-risk, medically ill patients, to describe drug exposure based on creatinine clearance (CrCl).

The Health Economics objective is to assess the following cost drivers, ie, re-hospitalization (including length of stay [LOS]), emergency room (ER) visits, intensive care unit (ICU) and cardiac care unit (CCU) stays, including LOS and subject discharge disposition between the 2 treatment groups.

The safety objectives are to compare rivaroxaban with placebo in the following bleeding outcomes in high-risk, medically ill patients:

- Major bleeding using validated International Society on Thrombosis and Haemostasis (ISTH) bleeding criteria.
- Non-major clinically relevant bleeding
- Other bleeding

Overall safety will also be assessed.

1.2. Trial Design

This is a multicenter, prospective, randomized, double-blind, placebo-controlled, event-driven study designed to evaluate rivaroxaban, compared with placebo, in the prevention of symptomatic VTE (lower extremity DVT and non-fatal PE) events and VTE-related deaths (death due to PE or death in which PE cannot be ruled out as the cause) for a period of 45 days post-hospital discharge. The first dose of study drug should be administered no later than the day after the subject leaves the hospital and as soon after randomization (Day 1) as possible. Subjects will be instructed to discontinue study drug after they take a dose on Day 45. The subject population comprises men and women age 40 and over who had been hospitalized for at least 3 and no more than 10 consecutive days prior to randomization for a specific acute medical illness and have other risk factors for VTE. Subjects who meet all of the inclusion and none of the exclusion criteria will be randomly assigned to receive rivaroxaban or placebo. Randomization should occur on the same day as or the day after the subject leaves the hospital, and may occur at the hospital, clinic, or other discharge destination. Subjects will be randomized by strata (by subjects with a CrCl ≥ 30 mL/min and < 50 mL/min versus subjects with CrCl ≥ 50 mL/min, and by country) by an interactive web response system (IWRS). After randomization, subjects will receive double-blind treatment with rivaroxaban 10 mg (7.5 mg for subjects with a CrCl ≥ 30 mL/min and < 50 mL/min) daily or matching placebo daily.

The targeted total number of primary efficacy outcome in this event-driven study is 161. It is estimated that a total of approximately 8,000 subjects will need to be randomized to either rivaroxaban or placebo in 1:1 ratio. This estimate is based on an estimated placebo incidence rate of the primary efficacy outcome of 2.5%. In the event that the actual observed blinded pooled event rate is lower than the assumed rate, more subjects may be enrolled to accumulate additional outcome events. Randomization in this study may be stopped at approximately 12,000 subjects for administrative considerations even if the targeted 161 events have not been observed by then. The total number of VTE-related death events may also be taken into account when deciding to stop randomization.

An interim analysis for futility will be conducted when approximately 50% of subjects with an adjudicated primary efficacy outcome have been observed (about 50% of the expected total number of events based on the actual observed blinded pooled event rate even if this event rate is lower than the assumed rate).

Prior to randomization, all subjects must have received treatment during the index hospitalization with LMWH or UFH. The study consists of a screening phase, a 45-day double-blind treatment phase, and a 30-day follow-up. The total duration for a subject who completes the study after randomization is expected to be 75 days.

If the subject permanently discontinues treatment before Day 45, he/she should be instructed to complete an unscheduled visit and the remaining scheduled visits, including the Day 7 and Day 21 visits (if not yet completed) and the Day 45 (+4d) and Day 75 (± 5 d) visits

If a subject withdraws consent from the study or is lost to follow-up, his or her vital status and outcomes will be collected at the day 75 (± 5 d) visit either by telephone or in person, or if applicable, by a review of subject's medical or public records unless this contact is not allowed by local regulations.

For population PK analyses, based on the model performance and high variability of the PK parameters observed in the MAGELLaN study, at the Day 7 visit 2 blood samples (at pre-dose; 1-4 hours after study drug administration) and again at Day 21 visit (Visit 4) 2 blood samples (at 3 to 7 and 7 to 12 hours after study drug administration) will be collected for each subject for about 600 subjects (300 rivaroxaban subjects [200 subjects in the 10 mg QD group and 100 subjects in the 7.5 mg QD group] and 300 in the placebo group). The sparse blood samples for PK analyses will be collected in selected sites only.

An Executive Committee (EC), an Independent Data Monitoring Committee (IDMC) and a Clinical Event Committee (CEC) will be commissioned for this study.

The EC has overall responsibility for the design, conduct and reporting of the study. The EC will monitor overall safety during the study and will receive any recommendations from the IDMC regarding possible additional analyses or modifications to the study and decide whether to accept them. The EC will oversee the implementation of any modifications to the study.

[figure not shown]
The IDMC will review unblinded safety data periodically to ensure the safety of study subjects. If necessary or requested by the IDMC, subject level unblinded data may be provided to the IDMC. In addition, the IDMC will review results of the planned interim analysis and make a recommendation whether the study should be terminated prematurely due to futility. Detailed stopping guidelines are specified in the section 3.

The Clinical Event Committee (CEC) will adjudicate all suspected outcome events in a consistent and unbiased manner according to the definitions in the CEC charter while blinded to treatment assignment.

All committees will be governed by separate charters.

A diagram of the study design is provided below in [Figure 1](#):

Figure 1: Schematic Overview of the Study Design by Country

1.3. Statistical Hypotheses for Trial Objectives

The primary statistical alternative hypothesis is that rivaroxaban is superior to placebo on the primary efficacy outcome, that is, time to event for the rivaroxaban group is stochastically later than that for the placebo group from randomization up to Day 45. More specifically, the survival function for the placebo group is lower than that for the rivaroxaban group. The null hypothesis is the negation of the alternative hypothesis, that is, the survival function for the placebo group is not lower than that for the rivaroxaban group. As a further illustration of the hypotheses, for the case where hazard functions are proportional, the above alternative hypothesis can be expressed as that the hazard ratio (HR) of rivaroxaban versus placebo is less than 1, and the null hypothesis is that the HR is at least 1.

The secondary hypotheses are that rivaroxaban is superior to placebo in the prevention of 1) VTE-related death (death due to PE or death in which PE cannot be ruled out as the cause), 2) symptomatic VTE (lower extremity DVT and non-fatal PE), 3) the composite of symptomatic VTE and ACM, 4) the composite of symptomatic VTE (lower extremity DVT and non-fatal PE), MI, non-hemorrhagic stroke and CV death (death due to a known CV cause and death in which a CV cause cannot be ruled out; by this definition, a VTE-related death is considered a CV death) and 5) ACM alone.

1.4. Sample Size Justification

This is an event driven study. The targeted total number of primary efficacy outcome is 161, based on the ITT analysis set and Up-to-Day-45 analysis phase. If a subject has multiple events, only the first is counted towards study size determination.

This targeted total number of events is determined using statistical software East 5.3 based on the primary efficacy analysis (defined later) and the following assumptions:

- 40% relative risk reduction (RRR) in the primary efficacy outcome based on the ITT analysis set and Up-to-Day-45 analysis phase (RRR is defined as 1 minus the hazard ratio (HR) of rivaroxaban versus placebo.)
- Power of 90% assuming the above RRR
- Two-sided significance level of 0.05.

To observe the targeted 161 events, it is estimated that a total of approximately 8,000 subjects will need to be randomized to either rivaroxaban or placebo in 1:1 ratio. This estimate is based on an estimated placebo incidence rate of the primary efficacy outcome of 2.5%. In the event that the actual observed blinded pooled event rate is lower than the assumed rate, more subjects may be enrolled to accumulate additional outcome events. Randomization in this study may be stopped at approximately 12,000 subjects for administrative considerations even if the targeted 161 events have not been observed by then. The total number of VTE-related death events may also be taken into account when deciding to stop randomization.

[Table 1](#) below additionally shows the approximate numbers of randomized subjects needed to observe 161 events based on several other placebo incidence rates.

Table 1: Approximate Number of Subjects Needed to Observe 161 Events

Placebo Incidence Rate	Number of Subjects*
3.0%	6,700
2.75%	7,300
2.5%	8,000
2.25%	9,000
2.0%	10,100
1.5%	13,400
1.25%	16,100
*calculated based on 40% RRR	

1.5. Randomization and Blinding

Central randomization will be implemented in this study. Subjects will be randomly assigned to 1 of 2 treatment groups based on a computer-generated randomization schedule prepared before the study under the supervision of the sponsor. The randomization will be balanced by using randomly permuted blocks and will be stratified by subjects with CrCl ≥ 30 and < 50 mL/min versus subjects with CrCl ≥ 50 ml/min and by country.

2. GENERAL ANALYSIS DEFINITIONS

Summaries by treatment group using appropriate descriptive statistics will be provided for all study variables including demographic and baseline characteristics. No imputation will be applied, unless specified otherwise in the SAP. Descriptive statistics such as mean, median, standard deviation, minimum, and maximum will be used to summarize continuous variables. Counts and percentages will be used to summarize categorical variables. Kaplan-Meier method will be used to summarize time-to-event variables. Graphical data displays may also be used to summarize the data.

Unless stated otherwise, subjects will be analyzed according to the treatment group they are assigned, irrespective of the actual treatment received.

Unless stated otherwise, all adjudicated efficacy and bleeding outcomes will be used in the analyses.

2.1. Definition of Trial Dates

Trial reference start date: the date of randomization of the subject.

Trial reference end date: the date of the last trial-related procedure for the subject and is defined as the maximum of the following dates:

- Dates of all study-related visits (including scheduled or unscheduled visits)
- Dates of all study-related procedures, findings and events, including, but not limited to, adverse events, concomitant medications, disposition, clinical laboratories, vital signs, death

First dose date: the date on which the first dose of study drug is taken by the subject. If missing or incomplete for a subject who takes study drug, the first dose date is set to the earliest logically possible date on or after randomization. More specifically, the first dose date is defined as the maximum of the randomization date and the first day of the month if only day is missing, and is defined as the randomization date if day and month are missing.

Last dose date: the date on which the last dose of study drug is taken by the subject. If missing or incomplete for a subject who takes study drug, the last dose date is in general set to the latest logically possible date on or after the first dose date.

To ensure consistency with other data of the trial, more specifically, the above date will be further

- capped by (that is, taking the minimum with) Day 45 date, death date, trial reference end date, and the upper bound of the logically possible range if partial date is available, and
- further bounded below by (that is, taking the maximum with) the (imputed) first dose date, any complete temporary drug stop and re-start date, or the lower bound of the logically possible range.

Upper bound of the logically possible range is defined as the last day of the month if only day is missing and is defined as the last day of the following month after randomization if day and month are missing. Lower bound of the logically possible range is defined the maximum of the randomization date and the first day of the month if only day is missing and is defined as the randomization date if day and month are missing.

Last outcome-evaluation date: the date of last study visit (clinic/phone) while the subject is alive during which the outcome status is ascertained.

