2.3. Analysis set and Analysis Phase

Each analysis involves the following 2 aspects: 1) analysis set, specifying the subjects to be included; and 2) analysis phase, specifying the time window within which data will be included.

Key analysis sets and analysis phases are defined below.

Analysis sets

- Intention-to-Treat (ITT) (as termed Full Analysis Set in the International Conference on Harmonisation [ICH] E9 guideline): This analysis set consists of all randomized subjects who have a signed valid informed consent.
- Per-Protocol (PP): This analysis set is a subset of the ITT analysis set.

Subjects with the key protocol deviations will be excluded from the PP analysis set. The categories and terms of the key protocol deviations will include the following:

- Did not meet the following inclusion or met the following exclusion criteria;
 - INT-2, INT-3, INT-4: subject with index hospitalization > 14 days, inclusion criteria 1, 2, 4, 6, exclusion criteria 10, 11, 14, 22, 24, 27
 - INT-6, INT-7: inclusion criteria 1.2, 2.2, 4.3, 6.1, exclusion criteria 10.2, 11.1, 14.1, 22.2, 24.2 without c
- Did not take any assigned study drug or took wrong study drug
- Did not discontinue study drug permanently according to the protocol (The subject becomes pregnant, develops any condition which requires permanent anticoagulation, has a fall in CrCl to below 20 mL/min during the study, or has a hemorrhagic stroke or intracranial bleeding)
- Had been taking prohibited concomitant therapies as specified in the protocol
 - INT-2: 2, 3,
 - INT-3, INT-4: 2, 3, 4, 6, 7, 8
 - INT-6, INT-7: 2.2, 3.2, 4.1, 7.1 without c and i

- Safety: This analysis set is a subset of the ITT analysis set, consisting of subjects who receive at least one dose of study drug.

Analysis phases

- Up-to-Day-45: This analysis phase includes all data from randomization to Day 45 (inclusive).

For time to event analyses, subjects who do not have events to be analyzed on or before Day 45 will be censored on Day 45 or the last outcome-evaluation date whichever occurs first.

- On-Treatment: This analysis phase includes all data from randomization to 2 days after the last dose of the study drug (inclusive).

For time to event analyses, subjects who do not have events to be analyzed during this phase will be censored on the last dose + 2 or the last outcome-evaluation date whichever occurs first.

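### For a last-dose date with only the year known, the SAP 2.1 upper bound can fall before Day 45, and even before the recorded year

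*SAP*

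**What the plan says.** SAP 2.1 (Definition of Trial Dates) handles a missing or incomplete last-dose date in three steps.

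- **Principle.** "the last dose date is in general set to the latest logically possible date on or after the first dose date".
- **Caps.** The result is "capped by (that is, taking the minimum with) Day 45 date, death date, trial reference end date". One more cap closes this list and is used for partial dates only: "and the upper bound of the logically possible range if partial date is available". If only the day is missing, the upper bound is the end of the recorded month. If day and month are both missing, it "is defined as the last day of the following month after randomization if day and month are missing".
- **Floors.** The maximum is then taken with "the (imputed) first dose date, any complete temporary drug stop and re-start date, or the lower bound of the logically possible range". With day and month missing, the lower bound is the randomization date.

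SAP 1.2 makes randomization Day 1 and fixes the planned end of dosing: "Subjects will be instructed to discontinue study drug after they take a dose on Day 45". Under SAP 2.3 the on-treatment phase, and censoring within it, run to two days after the last dose.

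**The concern.** The cap for year-only dates conflicts with the principle it is meant to serve. A subject randomized late in a month is due to take study drug beyond the end of the following month, so the cap rules out dates that are possible and indeed planned. It also takes no account of the year, which is the only part of the date that was recorded.

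The last-dose date feeds:

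- the on-treatment analysis of ISTH major bleeding (SAP 6.1);
- the per-protocol/on-treatment sensitivity analysis (SAP 5.2.2);
- treatment-emergent adverse events (SAP 6.2);
- treatment completion, compliance and exposure (SAP 4.2 to 4.4).

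If the imputed date is too early, a bleed that occurred on drug could be reported as off-treatment. Two subjects with equivalent data could also be treated differently only because of the day of the month on which they were randomized.

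**Working it through.** The plan states no figure here, so there is none to reproduce. The check is a calendar count.

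**Inputs.** Randomization is Day 1, so Day 45 is randomization + 44 days (SAP 1.2). The bound is the last day of the month after the month of randomization (SAP 2.1).

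**When the bound precedes Day 45.** Let L1 be the length of the randomization month, L2 the length of the next month, and d the day of the month. Counting from the start of the randomization month, the bound is day L1 + L2 and Day 45 is day d + 44. The bound is too early when d > L1 + L2 − 44. That gives L1 − (L1 + L2 − 44) = 44 − L2 affected dates per month, with shortfalls of 1, 2, …, 44 − L2 days. The first affected day of the month, L1 + L2 − 43, lies between the 16th and the 19th.

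Non-leap year:

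| Days in next month | Randomization months | Affected dates per month | Affected dates in total | Summed shortfall (days) |
|---|---|---|---|---|
| 28 | January | 16 | 16 | 136 |
| 30 | March, May, August, October | 14 | 56 | 4 × 105 = 420 |
| 31 | the other seven | 13 | 91 | 7 × 91 = 637 |
| Total | | | 163 | 1,193 |

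- Non-leap year: 163/365 = 44.7%.
- Leap year (January contributes 15 dates and 120 days): 162/366 = 44.3%, summed shortfall 1,177 days.
- Four years with one leap year: (3 × 163 + 162)/1,461 = 651/1,461 = 44.6%. Mean shortfall where the bound is too early: (3 × 1,193 + 1,177)/651 = 7.3 days.
- Worst case: randomized 31 January in a non-leap year. The bound is 28 February = Day 29, and Day 45 is 16 March, 16 days later.

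**Recorded year equal to the randomization year.** The latest possible date is then no later than 31 December. For November randomizations the bound is 31 December itself, and for December randomizations it is later, so the month-end rule removes nothing further in those months. That leaves 163 − 13 − 13 = 137 of 365 (37.5%), 136 of 366 (37.2%) in a leap year, and 547 of 1,461 (37.4%) over four years.

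**Recorded year equal to the next year.** This is possible within Day 45 for randomizations from 18 November to 31 December (13 + 31 = 44 dates). The bound precedes Day 45 for 26 of them. For the 13 November dates it also precedes the recorded year. Example: randomized 30 November 2016, last dose recorded as 2017.

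1. Latest date in the recorded year: 31 December 2017.
2. Minimum with Day 45: 13 January 2017.
3. Minimum with the bound: 31 December 2016, which is Day 32.
4. The floors (first dose; randomization) do not move it, absent a later complete stop or re-start date.

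The imputed date lies outside the year that was recorded.

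**Wholly missing date.** The bound applies only when a partial date exists. With no date information, the Day 45, death and trial-end caps alone apply, and the 30 November subject can reach 13 January 2017.

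**Effect on one subject, worst case.** The on-treatment phase ends on Day 29 + 2 = Day 31 instead of Day 45 + 2 = Day 47. Assuming a first dose on Day 1, no interruption, no death and no primary outcome, the SAP 4.3 compliance rate is 29/45 = 64%.

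**The case against.** The strongest reply is that this will rarely matter. Treatment lasts 45 days. Drug accountability is done at Days 21 and 45 (Protocol 7), the Day 21 visit should be in person (Protocol 9.1.3), interruptions are recorded in the eCRF (Protocol 6), and permanent discontinuation calls for an unscheduled visit (Protocol 10.2.3). A last-dose date known only to the year should be unusual, and a later complete stop or re-start date overrides the cap. The day of the month is also unrelated to randomized arm. All of this stands and limits the size of the point. It does not make the bound correct.

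Some stronger readings are tempting but not supported:

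- A reader might infer that about 45% of subjects or events are affected. The figure is a share of calendar randomization dates and matters only for year-only last-dose dates.
- A reader might infer that bleeds or VTE events are in fact moved off-treatment. With a year-only date, nobody knows whether the subject was still dosing, so the rule could reclassify events but need not.
- A reader might infer that a December randomization with that same year recorded is imputed into the next year (for example, randomized 5 December 2016, recorded 2016, imputed to Day 45 on 18 January 2017). Read literally, the starting value is already 31 December 2016, and taking minimums cannot move it later. The year conflict arises in the other direction, as in the November example.
- A reader might infer that the main efficacy result is at risk. The primary analysis (SAP 5.2.2) and the primary benefit-risk analysis (SAP 7) use the ITT set and the Up-to-Day-45 phase, which do not depend on the last-dose date.

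**Conclusion.** The concern holds as an internal contradiction in a data-handling rule, and it is minor. For year-only last-dose dates the stated upper bound precedes Day 45 for 44.6% of randomization dates, or shortens the date for about 37% when the recorded year is the randomization year. It can also place the imputed date before the recorded year. The practical effect is confined to year-only dates without a later complete stop or re-start date, and to analyses that use the last-dose date. The percentages rest on randomization being Day 1 and on weighting calendar dates equally. The documents do not give the number of year-only dates; that it is small is a judgement.

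**What to change.** In SAP 2.1, for a last-dose date with day and month missing, define the upper bound as 31 December of the recorded year and the lower bound as the later of the randomization date and 1 January of the recorded year. Keep the Day 45, death and trial-end caps. The 30 November 2016 subject then receives 13 January 2017, and the month-end rule no longer shortens any date. A recorded year that contains no date between randomization and Day 45 should be queried as a data error before the rule is applied.

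The cost is one sentence in the SAP and a small programming change, to be made before unblinding. No endpoint or test changes. There is a minor downside: some subjects who stopped early would be credited with on-treatment time up to Day 45. The SAP's choice of the latest possible date already accepts this.
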